#### 6.4 Follow-up Period after EOT or Early Termination of study medication

Patients who discontinue study medication early (before week 52) will have an EOT visit and then a 4 week follow-up visit. They will then be followed up at a reduced visit schedule of every 8 weeks until the end of the study (see [Table 2](#)).

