**Appendix B - Patients who Discontinue Study Medication Prior to Week 52**

Procedures	EOT 	Post - EOT 	Every 8 weeks assessment from Post-EOT WK 4 visit. Last visit at Week 52 from first dose.	
		WK 4	WK 12	→
Informed consent signature				
Eligibility Review 				
Med History/ Demographics				
Physical Exam	X	X		
Weight 				
HbsAg, anti-HCV AB, HIV				
Endogenous serum EPO Level 	X	X	X	
B12, Folate	X	X		
PK 				
ECG 	X	X		
Bone marrow aspirate and biopsy 	X			
Vital signs 	X	X	X	
ECOG Score 	X	X		
Serum Lipid Panel	X	X		
LFTs 	X	X	X	
Serum chemistry 	X	X	X	
PT, PTT	X	X		
Hepcidin	X	X	X	
Pregnancy test 	X	X		
C-reactive protein	X	X		
Recording of transfusions 	→			
CBC 	X	X	X	
Local Hemoglobin	X	X	X	
Reticulocyte count; CHr	X	X		
Iron Biomarkers 	X	X	X	
Registration/Randomization to the study				
HRQoL Questionnaires 	X	X		
Study drug dosing				
Study drug dispensation				
Dose adjustment review				
AEs/Con Meds/Procedures	→			

For footnotes please refer to [Appendix A](#)

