Week 28 visit: Week 28 visit should be conducted at the end of 28 weeks of treatment (2 weeks after Week 27 Visit). Primary analysis of efficacy will be conducted when all the randomized (DB) patients complete 28 weeks of treatment or are discontinued from study medication before this time. **End-of-Treatment (EOT/ET) Visit:** Patients who complete 52-week treatment period or discontinue study medication early (Early Termination before week 52) will have an EOT/ET visit.

Post-Treatment Follow-Up Period: Week 56 (Post-EOT Week 4)

Post-Treatment Follow-Up Period for ET Patients: Patients who discontinue early will have visits every 8 weeks until Week 52.

End of Study (EOS) Visit: All patients who complete 52 weeks (of treatment with study medication) will undergo a 4 week follow-up period after the last dose of study medication and will return for the End of Study (EOS) visit. Patients who discontinue study medication early (for any reason) will remain in the study through the entire 52 week study period. Patients will have a 4 week follow-up visit after stopping study medication/ET visit and then be followed up at a reduced visit schedule of every 8 weeks until the end of the study.

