Week 9 and week 52 are the analysis endpoint for 28-week and 52-week analysis respectively, the p-value obtained will be reported.

This analysis will take into account the potential intercurrent events as follows:

1. Treatment discontinuation due to reasons other than AE/SAE: using Treatment-policy strategy: regardless of these intercurrent events occurred;
2. Treatment discontinuation due to AE/SAE: using Hypothetical strategy: A scenario is envisaged in which the patient suffers from the worst quality of life after discontinuation treatment due to AE/SAE. If a patient discontinued treatment due to AE/SAE, all the missing PROMIS-SF v2.0 Physical Function 10b score afterward will be substituted with the worst possible scores before being used in descriptive summary and statistical models.
3. Death: using Treatment-policy strategy: regardless of these intercurrent events occurred. If a patient died, the PROMIS-SF v2.0 Physical Function 10b scores up to death will be used for analysis.

Line plot of mean and mean change from baseline over time with the associated standard error will be provided. A cumulative distribute plot will be presented to show the difference of patients achieving meaningful change in PROMIS-SF v2.0 Physical Function 10b score between two treatment groups.

A by-patient listing will also be provided.

The analysis will be conducted for FAS and PPS.

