19.3. Data Handling Conventions

19.3.1. Analysis Windows

Tables below present the visits assigned for efficacy and safety analyses corresponding to the range of treatment days (window) during which an actual visit may have occurred.

The analysis windows will be only applied to those assessments up to the day before the first week of follow-up visit. Assessments obtained afterwards are considered follow-up assessments. For follow-up assessments, only follow-up assessments on scheduled follow-up visits (i.e. nominal follow-up visits) will be summarized unless otherwise specified.

If more than one assessment is available in the same window, the last assessment is used for analysis. Assessments that do not fall in any windows will not be included in analyses unless otherwise specified. However, all post-baseline assessments will be used for PCS value determination and all assessments will be presented in the data listings.

Table 7.1 Analysis Visit Windows (General)

Analysis Visit	Visit Scheduled Day ^a	Window
Baseline	Day 1	Up to Day 1 Pre-Dose
Week 3	Day 7*(Week # -1)+1	[Day 1 Post-Dose, Scheduled Day +7)
Weeks 5, 7, 9, 11...27	Day 7*(Week # -1)+1	[Scheduled Day -7, Scheduled Day +7)
Week 28 ^b	Day 7*(Week #)+1	[Scheduled Day -7, Scheduled Day +7)
Weeks 31	Day 7*(Week # -1)+1	[Scheduled Day -7, Scheduled Day +14)
Week 35, 39, 43	Day 7*(Week # -1)+1	[Scheduled Day -14, Scheduled Day +14)
Week 47	Day 7*(Week # -1)+1	[Scheduled Day -14, Scheduled Day +21)
Week 52 ^c	Day 7*(Week #)+1	[Scheduled Day -21, Up to Week 4 Follow up)

^a: Relative to the first study medication date. For example, Day 1 = the first dose date of study medication.

^b: Week 28 visit should be conducted at the end of 28 weeks of treatment (2 weeks after Week 27 Visit).

^c: Week 52 Visit should be scheduled at the end of 52 weeks treatment (6 weeks after Week 47 visit).

Table 7.2 Analysis Visit Windows for Lipid Parameters

Derived Visit	Visit Scheduled Day ^a	Window
Baseline	Day 1(first dose day)	Up to Day 1 Pre-Dose
Week 5	Day 7 * (Week # -1) +1	[Day 1 Post-dose, Scheduled Day + 56)
Week 21	Day 7 * (Week # -1) +1	[Scheduled Day - 56, Scheduled Day + 28)
Week 28 ^b	Day 7 * (Week #) +1	[Scheduled Day - 28, Scheduled Day + 35)
Week 39	Day 7 * (Week # -1) +1	[Scheduled Day - 35, Scheduled Day + 49)
Week 52 ^c	Day 7 * (Week #) +1	[Scheduled Day -49, Up to Week 4 follow-up)

^a: Relative to the first study medication date. For example, Day 1 = the first dose date of study medication.

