^a: Relative to the first study medication date. For example, Day 1 = the first dose date of study medication.

^b: Week 28 visit should be conducted at the end of 28 weeks of treatment (2 weeks after Week 27 Visit).

^c: Week 52 Visit should be scheduled at the end of 52 weeks treatment (6 weeks after Week 47 visit).

**Table 7.6 Analysis Visit Windows for CBC
(Only in Subjects Enrolled before Effective Day of Protocol Amendment 3)**

Analysis Visit	Visit Scheduled Day ^a	Window
Baseline	Day 1	Up to Day 1 Pre-Dose
Week 2	Day 7*(Week # -1)+1	[Day 1 Post-Dose, Scheduled Day +3]
Week 3,4	Day 7*(Week # -1)+1	[Scheduled Day -3, Scheduled Day +3]
Week 5	Day 7*(Week # -1)+1	[Scheduled Day -3, Scheduled Day +7]
Weeks 7, 9, 11...27	Day 7*(Week # -1)+1	[Scheduled Day -7, Scheduled Day +7]
Week 28 ^b	Day 7*(Week #)+1	[Scheduled Day -7, Scheduled Day +7]
Weeks 31	Day 7*(Week # -1)+1	[Scheduled Day -7, Scheduled Day +14]
Week 35, 39, 43	Day 7*(Week # -1)+1	[Scheduled Day -14, Scheduled Day +14]
Week 47	Day 7*(Week # -1)+1	[Scheduled Day -14, Scheduled Day +21]
Week 52 ^c	Day 7*(Week #)+1	[Scheduled Day -21, Up to Week 4 Follow up)

^a: Relative to the first study medication date. For example, Day 1 = the first dose date of study medication.

^b: Week 28 visit should be conducted at the end of 28 weeks of treatment (2 weeks after Week 27 Visit).

^c: Week 52 Visit should be scheduled at the end of 52 weeks treatment (6 weeks after Week 47 visit).

Table 7.7 Analysis Visit Windows for EQ-5D-5L, PROMIS Physical Function and PROMIS Fatigue Function

Derived Visit	Visit Scheduled Day ^a	Window
Baseline	Day 1(first dose day)	Up to Day 1 Pre-Dose
Week 9	Day 7 * (Week # -1) +1	[Day 1 post-dose, Scheduled Day + 28)
Weeks 17	Day 7 * (Week # -1) +1	[Scheduled Day - 28, Scheduled Day + 42)
Week 28 ^b	Day 7 * (Week #) +1	[Scheduled Day - 42, Scheduled Day + 84)
Week 52 ^c	Day 7 * (Week #) +1	[Scheduled Day - 84, Up to Week 4 follow-up)

^a: Relative to the first study medication date. For example, Day 1 = the first dose date of study medication.

^b: Week 28 visit should be conducted at the end of 28 weeks of treatment (2 weeks after Week 27 Visit).

^c: Week 52 Visit should be scheduled at the end of 52 weeks treatment (6 weeks after Week 47 visit).

Table 7.8 Analysis Visit Windows for ECOG

Derived Visit	Visit Scheduled Day ^a	Window
Baseline	Day 1(first dose day)	Up to Day 1 Pre-Dose
Week 5	Day 7 * (Week # -1) +1	[Day 1 post-dose, Scheduled Day + 28)

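### An end-of-treatment questionnaire on Days 1 to 84 counts as Week 9, so AE/SAE discontinuers who complete one escape the worst-score rule at the time point used in Tests 8 to 10

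*SAP*

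**What the plan says.** **Windows.** SAP 19.3.1 assigns analysis visits by treatment day, "corresponding to the range of treatment days (window) during which an actual visit may have occurred". For EQ-5D-5L and both PROMIS scales, Table 7.7 gives Week 9 the window "Day 1 post-dose, Scheduled Day + 28". Two general rules apply:
- "The analysis windows will be only applied to those assessments up to the day before the first week of follow-up visit"
- "If more than one assessment is available in the same window, the last assessment is used for analysis"

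**Early stoppers.** Protocol 6.4 says "Patients who discontinue study medication early (before week 52) will have an EOT visit and then a 4 week follow-up visit", and SAP 3.1 likewise says that patients who "discontinue study medication early (Early Termination before week 52) will have an EOT/ET visit". In Protocol Appendix B the row "HRQoL Questionnaires" is marked at EOT and at the 4-week post-EOT visit, but not at the 8-weekly visits after that.

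**Substitution.** For patients who stop because of an AE/SAE, SAP 12.3.3.6 envisages the worst quality of life after discontinuation. It carries this out by saying that "all the missing PROMIS-SF v2.0 Physical Function 10b score afterward will be substituted with the worst possible scores". SAP 12.3.3.7 (Fatigue) and 12.3.3.8 (VAS) use the same rule, also limited to missing scores.

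**Tests.** In SAP Table 4, Tests 8, 9 and 10 are the Week 9 changes in Physical Function, Fatigue and VAS.

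**The concern.** The window rule and the substitution rule are each clear alone, but together they give a result that the estimand does not describe. For a patient who stops early for an AE/SAE, the Week 9 value depends on whether an EOT form was completed in the window, not on the intercurrent event. A patient with a form contributes an observed score from the day of stopping. An otherwise identical patient without one contributes the worst score on the scale.

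SAP Section 17 chose Week 9 to catch the effect shortly after haemoglobin peaks or stabilises. A form from the second or third week of treatment does not serve that purpose.

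At stake are three alpha-controlled comparisons. The LOCF sensitivity analysis in SAP 19.8.2 is run after the intercurrent-event handling, so it inherits the same values for Tests 8 and 9.

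**Working it through.** The SAP gives no sample size or power for Tests 8 to 10, so there is no stated figure to reproduce.

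**1. Windows from Table 7.7**
- Week 9: scheduled Day 7 × (9 − 1) + 1 = 57; window Day 1 to 57 + 28 = 85, exclusive, so Days 1 to 84.
- Week 17: scheduled Day 113; window [85, 155).
- Week 28: scheduled Day 7 × 28 + 1 = 197; window [155, 281).
- Week 52: scheduled Day 365; window opens on Day 281.

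The windows are contiguous, so the Day 1 start is what the table intends.

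**2. Following single patients through the rules**
- *AE stop, EOT form on Day 15.* The form precedes follow-up, so it is windowed, and it falls in Days 1 to 84. Week 9 is not missing and gets no substitution. Weeks 17, 28 and 52 are missing and get the worst score.
- *Same patient, no EOT form.* The 4-week post-EOT form is a follow-up assessment and is not windowed. Week 9 is missing and is set to 13.8 (Physical Function), 83.5 (Fatigue) or 0 (VAS).
- *AE stop, EOT form on Day 40, before the Week 9 visit.* Same outcome as Day 15. A window of Days 29 to 84 would still capture this form.
- *Week 9 form on Day 57, EOT form on Day 70.* The last-in-window rule discards the genuine Week 9 form.

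The worst scores come from the conversion tables in SAP 19.5 and 19.6 and the VAS description in 12.3.3.8. For Fatigue I follow the item coding in 19.6, where more fatigue scores higher. SAP 12.3.3.7 describes the direction the other way.

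**3. Size**

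Let p be the share of an arm that stops for an AE/SAE before Week 9 and has an EOT form in the window.

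Shift in treatment difference = (p_roxadustat − p_placebo) × (EOT score − worst score)

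The rates and EOT scores are assumptions. The central EOT scores are 40, 55 and 60; the brackets cover EOT scores of 30 to 50, 50 to 65 and 40 to 70. Shifts are absolute values.

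| Scale | Gap at central score | 5% vs 2% | 8% vs 2% |
|---|---|---|---|
| Physical Function | 40 − 13.8 = 26.2 | 0.03 × 26.2 = 0.79 (0.49 to 1.09) | 0.06 × 26.2 = 1.57 (0.97 to 2.17) |
| Fatigue | 83.5 − 55 = 28.5 | 0.03 × 28.5 = 0.86 (0.56 to 1.01) | 0.06 × 28.5 = 1.71 (1.11 to 2.01) |
| VAS | 60 − 0 = 60 | 0.03 × 60 = 1.8 (1.2 to 2.1) | 0.06 × 60 = 3.6 (2.4 to 4.2) |

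In these examples the rules as written favour roxadustat by the amounts shown, relative to full substitution. At equal rates the shift is 0. At 2% vs 5% it is 0.79, 0.86 and 1.8 in the other direction.

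The 140 patients enrolled would split 84:56 at exactly 3:2. On that split, one affected patient with a Physical Function score of 40 moves the arm mean by 26.2/84 = 0.31 on roxadustat or 26.2/56 = 0.47 on placebo.

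**The case against.** **The rule covers only missing scores.** An EOT form is an observed score, so using it follows the operative sentence. This stands as a reading of that sentence. It does not fit the scenario in the same paragraph, nor does it explain why two patients with the same event should be treated so differently. Overriding an observed form is a choice of strategy, and the SAP should state it as one.

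**Other readings could rescue the plan.** Substitution at the scheduled Week 9 visit could come first, so that the Day 57 worst score follows a Day 15 form and wins as the last value. Alternatively, EOT could be mapped to Week 52, because the schedule in 12.3.3.6 lists Week 52 (or EOT). The SAP states neither. Its table is based on days, and the Week 52 window opens only on Day 281.

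**Starting the first window at Day 1 is a convention across Tables 7.1 to 7.8.** This is correct. It shows that the lower bound is not the root of the problem, and step 2 shows that moving it would not be a cure.

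**A reader might infer that the worst-score rule never operates in Tests 8 to 10.** The documents do not support that. AE/SAE discontinuers with no form on Days 1 to 84 still get the worst score at Week 9. No questionnaire is scheduled between Day 1 and Week 9, so patients still on treatment at Week 9 are affected only if an unscheduled or later EOT form falls in the window.

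**Conclusion.** The point holds on the text. For patients who stop for an AE/SAE before the Week 9 visit and complete an EOT questionnaire on Days 1 to 84, the SAP's own rules leave the worst-score substitution unapplied at the time point tested. The later visits are still substituted.

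A reader might also infer a bias in favour of roxadustat. The documents give no AE discontinuation rates by arm, so neither direction nor size is known. On the assumptions shown, the difference shifts by about 0.8 to 1.6 Physical Function T-points, 0.9 to 1.7 Fatigue T-points and 1.8 to 3.6 VAS points as the roxadustat rate goes from 5% to 8% against 2% on placebo. It is zero at equal rates and reverses if placebo is higher. These are raw-mean approximations; the tests themselves use an MMRM.

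The reach is limited. Tests 8 to 10 are formally tested only if Tests 1 to 7 succeed, and the primary endpoint is not affected. The wording should still be settled before unblinding, because the result of a confirmatory test should not depend on whether a form was completed or on how a programmer orders two steps.

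**What to change.** State the following in SAP 12.3.3.6 to 12.3.3.8 and in 19.3.1:

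1. For patients who stop treatment because of an AE/SAE, every questionnaire visit scheduled after the discontinuation date is treated as missing and receives the worst score.
2. An EOT form does not count as such a visit.
3. This substitution is made before the last-in-window rule is applied.
4. An EOT form never displaces a genuine Week 9 form.

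Starting the Week 9 window at Day 29 is an optional addition. Alone it does not solve the problem, because EOT forms on Days 29 to 84 would still be taken as Week 9. It also has a price: very early forms would leave the Week 9 analysis, including those of patients who stopped for other reasons and are meant to be handled under treatment policy.

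The cost is a few sentences in the SAP and the matching programming specification. No new data are needed. The main consequence to accept is that some observed EOT scores will not be used at Week 9 for AE/SAE discontinuers.

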19.3.2. Missing Date of Study Medication

When the last date of study medication during the study treatment period is missing, all efforts should be made to obtain the date from the investigator. If it is still missing after all efforts, then the last visit date during the treatment period will be used in the calculation of treatment duration.

19.3.3. Missing Severity Assessment for Adverse Events

If severity is missing for an AE started prior to the first study medication, then a severity of “Mild” will be assigned. If the severity is missing for an AE started on or after the first study medication dosing, then a severity of “Severe” will be assigned. The imputed values for severity assessment will be used for incidence summary, while the actual missing values will be presented in data listings.

19.3.4. Missing Relationship to Study Drug for Adverse Events

If the relationship to the study medication is missing for an AE started after baseline, a causality of “possibly related” will be assigned. The imputed values for relationship to study medication will be used for incidence summary, while the actual values will be presented in data listings.

19.3.5. Missing Date Information for Adverse Events

The following imputation rules only apply to the case where the start date is incomplete (i.e., partial missing) for adverse events.

Missing day and month

If the year is same as the year of first day on study medication, then the day and month of the start date of study medication will be assigned to the missing fields.

If the year is prior to the year of first day on study medication, then December 31 will be assigned to the missing fields.

If the year is after the year of first day on study medication, then January 1 will be assigned to the missing fields.

Missing month only

Treat day as missing and replace both month and day according to the above procedure.

Missing day only

If the month and year are same as the year and month of first day on study medication, then the start date of study medication will be assigned to the missing day.

If the month and year are before the year and month of first day on study medication, then the last day of the month will be assigned to the missing day.

If the month and year are after the year and month of first day on study medication, then the first day of the month will be assigned to the missing day.

If the stop date is complete and the imputed start date as above is after the stop date, the start date will be imputed by the stop date.

19.3.6. Missing Date Information for Prior or Concomitant Medications

For prior or concomitant medications, including rescue medications, incomplete (i.e., partial missing) start date and/or stop date will be imputed. When the start date and the stop date are both incomplete for a patient, impute the start date first.

Incomplete Start Date

The following rules will be applied to impute the missing numerical fields. If the stop date is complete and the imputed start date is after the stop date, then the start date will be imputed using the stop date.

Missing day and month

If the year of the incomplete start date is the same as the year of the first dose date of study medication, then the day and month of the first dose date will be assigned to the missing fields.

If the year of the incomplete start date is prior to the year of the first dose date of study medication, then December 31 will be assigned to the missing fields.

If the year of the incomplete start date is after the year of the first dose date of study medication, then January 1 will be assigned to the missing fields.

Missing month only

Treat day as missing and replace both month and day according to the above procedure.

Missing day only

If the month and year of the incomplete start date are the same as the month and year of the first dose date of study medication, then the day of the first dose date will be assigned to the missing day.

If either the year is before the year of the first dose date of study medication or if both years are the same but the month is before the month of the first dose date of study medication, then the last day of the month will be assigned to the missing day.

If either the year is after the year of the first dose date of study medication or if both years are the same but the month is after the month of the first dose date of study medication, then the first day of the month will be assigned to the missing day.

Incomplete Stop Date

The following rules will be applied to impute the missing numerical fields. If the last dose date of study medication is missing, replace it with the last visit date. If the imputed stop date is before the start date (imputed or non-imputed start date), then the imputed stop date will be equal to the start date.

Missing day and month

If the year of the incomplete stop date is the same as the year of the last dose date of study medication, then the day and month of the last dose date will be assigned to the missing fields.

If the year of the incomplete stop date is prior to the year of the last dose date of study medication, then December 31 will be assigned to the missing fields.

If the year of the incomplete stop date is after the year of the last dose date of study medication, then January 1 will be assigned to the missing fields.

Missing month only

Treat day as missing and replace both month and day according to the above procedure.

Missing day only

If the month and year of the incomplete stop date are the same as the month and year of the last dose date of study medication, then the day of the last dose date will be assigned to the missing day.

If either the year is before the year of the last dose date of study medication or if both years are the same but the month is before the month of the last dose date of study medication, then the last day of the month will be assigned to the missing day.

If either the year is after the year of the last dose date of study medication or if both years are the same but the month is after the month of the last dose date of study medication, then the first day of the month will be assigned to the missing day.

19.3.7. Missing Start Date for Study Disease (Myelodysplastic Syndrome)

When start date of study disease (Myelodysplastic syndrome) is incomplete, the following imputation rules will be adopted:

Missing day and month

January 1 will be assigned to the missing fields.

Missing month only

January will be assigned to the missing month.

Missing day only

The first day of the month will be assigned to the missing day.

